### **3. Revision History**

Statistical analysis plan (SAP) Version 1 was approved prior to unblinding data for Study H0P-MC-NP02 (NP02).

SAP Version 2 was approved prior to unblinding data for Interim lock. Major revisions included:

Section 6.9: language indicating that electronic Clinical Outcome Assessments (eCOA) compliance is described in the H0P-MC-CPMP SAP version 5 was added.

Section 6.15: added language to allow the planned interim analysis to additionally modify the final sample size and added flexible language that allows for multiple interim analyses to be conducted.

Section 6.17:

Liver Function domain called drug-induced liver injury (DILI).

## 4. Study Objectives

### 4.1. Primary Objective

The primary objective of this intervention-specific appendix (ISA) is stated in the H0P-MC-CPMP (a) protocol. Additional blinded details regarding LY3526318 dosing that are not included in the protocol can be found in the Ethics Review Board (ERB) supplement for Study NP02. For Study NP02, endpoint is defined as 4 weeks post initial treatment administration at Visit 5. Unless otherwise specified, the time point for secondary endpoint measurements is the same as the primary endpoint.

Objectives	Endpoint
Primary	
Efficacy of LY3526318 versus placebo for pain intensity	Mean change from baseline assessment to 4 weeks for average pain intensity as measured by the NRS

Abbreviation: NRS = Numeric Rating Scale.

### 4.2. Secondary Objectives

Secondary objectives applicable to all ISAs are listed in the Study H0P-MC-CPMP (CPMP) SAP Version 5.

Additional secondary endpoints specific to Study NP02 are listed below.

Objective	Endpoint Measure
Other Secondary	
Physical Functioning Efficacy of LY3526318 versus placebo	
Mean change from baseline to endpoint for the Brief Pain Inventory-Short Form (BPI-SF) for the
 
 
○ Mean interference score
 
○ Mean severity score
 
○ Individual severity scores
 
○ Individual interference scores
 
 
Proportion of participants with reduction from baseline greater than or equal to 30%, 50%, and 70% on BPI-SF for the
 
 
○ Mean interference score
 
○ Mean severity Score
 
○ Individual severity scores
 
○ Individual interference scores
 

### 4.3. Exploratory Objectives

The following exploratory objectives and endpoints are specific to Study NP02.

Objectives	Endpoints
Tertiary/Exploratory	
Measure the pharmacokinetics of LY3526318 in participants with DPNP	Measure of plasma concentrations of LY3526318 to enable pharmacokinetic evaluations
(Duration of Response) Efficacy of LY3526318 versus Placebo	Mean change from baseline assessment up to 8 weeks for average pain intensity as measured by NRS

CCI

Abbreviations: DPNP = diabetic peripheral neuropathic pain; NRS = numeric rating scale.

## 5. Study Design

### 5.1. Summary of Study Design

The CPMP protocol provides a summary of the overall study design for the chronic pain master protocol. ISA-specific study design is provided in the NP02 protocol.

In this ISA, patients in the LY3526318 treatment arm receive LY3526318 for the first 4 weeks of the double-blind period (active-treatment period) and switch to placebo for the last 4 weeks of the double-blind period (post-active-treatment period) starting on the day of Visit 5. Placebo patients receive placebo for the entire 8-week double-blind period. Additional details of the study design may be found in the ERB supplement for Study NP02.

For the analyses listed in this SAP, except for treatment compliance, we define active treatment period and post-active treatment period as follows. The first 4 weeks of the double-blind period (active treatment period) ends at the day of Visit 5. The last 4 weeks of the double-blind period (post-active treatment period) begins the day after Visit 5.

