### 6.12.1. Extent of Exposure

Duration of exposure (defined as time since first dose of study treatment to last dose of study treatment in days) to study drug will be summarized by treatment group using descriptive statistics; the summary will also include the total exposure in patient years. Extent of exposure will be reported separately for the first 4 weeks (active treatment) and the last 4 weeks (post-active treatment) of the double-blind period. All patients will receive placebo starting the day of Visit 5.

Duration of exposure (days):

1. For the first 4-week active treatment period:  
= Date of last dose during the active treatment period   Date of first dose for the active treatment period + 1
2. For the last 4-week post-active treatment period:  
= Date of last dose during the post-active treatment period   Date of first dose for the post-active treatment period + 1

Total exposure in patient years will be calculated as follows:

Total exposure in patient years = Sum of duration (days) of exposures for all patients in the treatment group/365.25.

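### SAP 5.1 keeps the Visit 5 day in the active period for exposure, so 6.12.1 as written counts one placebo day as active exposure in the LY3526318 arm

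*SAP*

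**What the plan says.** SAP 5.1 defines the two treatment periods once for the whole plan, with a single exception: "For the analyses listed in this SAP, except for treatment compliance". Under that definition, "The first 4 weeks of the double-blind period (active treatment period) ends at the day of Visit 5" and "The last 4 weeks of the double-blind period (post-active treatment period) begins the day after Visit 5". The Visit 5 day therefore belongs to the active period.

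The preceding paragraph of 5.1 describes the treatment actually given. LY3526318-arm participants "switch to placebo for the last 4 weeks of the double-blind period (post-active-treatment period) starting on the day of Visit 5". SAP 6.12.1 repeats this for both arms: "All patients will receive placebo starting the day of Visit 5".

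SAP 6.12.1 then gives the exposure formulas. Active exposure is "Date of last dose during the active treatment period" minus the first dose date of that period, plus 1. Post-active exposure is the last dose date of that period minus "Date of first dose for the post-active treatment period + 1". Results are summarized by treatment group and by period, and "the summary will also include the total exposure in patient years".

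SAP 6.8, the one exempted analysis, leaves the Visit 5 day out of the first 4 weeks and includes it in the last 4. SAP 6.12.2 counts an adverse event as post-active only after Visit 5.

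In the protocol, the Schedule of Activities (1.3) marks study intervention at Visit 5 and asks participants to delay the dose on the days of Visits 4 to 7 until the blood sample has been taken. Section 4.1 also has participants continue study intervention at Visit 5.

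**The concern.** Extent of exposure is a dose-based summary, so its boundary should follow the dose. The rule in 5.1 instead follows the visit, which puts the first placebo dose inside the active period. Section 6.8 handles this boundary for compliance by moving the Visit 5 day to the second period, but exposure was not given the same treatment.

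Two things are at stake. The LY3526318 arm's active-period duration and patient-years would include a day without active drug for each participant dosed on the Visit 5 day. In addition, the compliance and exposure tables would use the same label, first 4 weeks, for different sets of days.

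**Working it through.** The documents give no exposure figure to reproduce, so the check is date arithmetic on the 6.12.1 formulas.

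**Inputs**

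- First dose at Visit 3, taken as Day 1 (day numbering is an assumption).
- Visit 5 at Week 4 (SAP 4.1; protocol 1.3), so Day 29 at nominal timing. With the ±3-day visit window, Day 26 to Day 32. The window is printed once in the schedule; applying it to Visit 5 is a reading of that table.
- Placebo from the Visit 5 day (SAP 5.1 and 6.12.1).
- Daily dosing with none missed around Visit 5 (assumption).
- About 150 randomized, about 85% expected to complete (SAP 5.2). The allocation ratio is redacted, so LY3526318 arm sizes of 50 to 100 (1:2 to 2:1) are assumed.

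**Active exposure per participant**

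Let Visit 5 fall on Day v. LY3526318 is taken on Days 1 to v − 1.

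- Literal rule, last dose on Day v: v − 1 + 1 = v days.
- Cut before the Visit 5 day, as in 6.8: (v − 1) − 1 + 1 = v − 1 days.

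| Visit 5 day | Literal | Cut as in 6.8 | Excess |
|---|---|---|---|
| 26 | 26 | 25 | 1/25 = 4.00% |
| 29 | 29 | 28 | 1/28 = 3.57% |
| 32 | 32 | 31 | 1/31 = 3.23% |

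**Arm total in patient-years**

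The excess is n/365.25, where n is the number of LY3526318-arm participants dosed on the Visit 5 day. For one participant it is 1/365.25 = 0.0027. At nominal timing:

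| n | Literal: n × 29/365.25 | Cut as in 6.8: n × 28/365.25 | Excess |
|---|---|---|---|
| 50 | 3.970 | 3.833 | 0.137 |
| 75 | 5.955 | 5.749 | 0.205 |
| 100 | 7.940 | 7.666 | 0.274 |

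If the whole expected 15% dropout fell before Visit 5, n would be 50 × 0.85 = 42.5 to 100 × 0.85 = 85, and the excess 0.116 to 0.233.

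**Post-active exposure per participant, Visit 5 on Day 29 and Visit 7 on Day 57**

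- Last dose on Day 56 (no Visit 7 dose): literal 56 − 30 + 1 = 27 days, against 56 − 29 + 1 = 28. The two periods sum to 56 either way.
- Last dose on Day 57 (Visit 7 dose taken): literal 57 − 30 + 1 = 28 days, against 57 − 29 + 1 = 29. The sum is 57 either way.

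Post-active exposure is one day short in both cases. Which count applies cannot be settled from the documents: the schedule in protocol 1.3 marks study intervention at Visit 7, and its sampling note covers a dose on that day, while protocol 4.1 says continued study intervention does not apply at Visit 7. Those passages must be reconciled, but the Visit 5 point does not depend on the outcome.

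**The case against.** The strongest objection concerns intent. Section 6.12.1 says just before the formulas that everyone receives placebo from the Visit 5 day, and a programmer could take this as the cut-off. The second formula also speaks of the first dose for the post-active period rather than during it, so the Visit 5 dose could be read as that first dose. The intent is plausible. But the sentence says what is given; it does not redefine the period that the formula uses, and the wording of the second formula does not override an explicit start on the following day. One programmer would obtain 29 days and another 28.

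A second objection is that one boundary for exposure and adverse events keeps their windows aligned. This has merit: the 5.1 boundary is reasonable for adverse events and for pre-dose Visit 5 measurements. It does not justify counting a placebo dose as active exposure.

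Third, a participant who doses at home before the visit, from earlier supply, would presumably take LY3526318, and the proposed cut would drop that active day. This is so, but such dosing departs from the schedule, and 6.8 already treats the day the same way.

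Fourth, the ethics board supplement, the master-protocol SAP or CRF dose dates tied to dispensed supply might lead to the right split. These cannot be seen here, and nothing in the available text says that they override 5.1.

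Finally, the effect is very small. That stands, and it limits the severity.

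**Conclusion.** The concern holds as a minor error in the written rule. Each LY3526318-arm participant dosed on the Visit 5 day gains one day of active exposure that is placebo: +3.6% at nominal timing, and +4.0% to +3.2% across the visit window. The arm total is overstated by about 0.14 to 0.27 patient-years under the assumed arm sizes, or 0.12 to 0.23 if all expected dropout precedes Visit 5.

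Participants who stop before Visit 5 are unaffected. In the placebo arm the day only moves between periods. The summary is descriptive, and no efficacy or safety conclusion changes.

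**What to change.** In SAP 5.1, extend the compliance exception to extent of exposure. In 6.12.1, state that active exposure ends with the last dose before the day of Visit 5 and that post-active exposure starts on that day, matching 6.8. Keep the 5.1 boundary for adverse events and pre-dose Visit 5 measurements.

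The cost is one clause, one sentence, a one-day date cut in the exposure program and a table footnote. No new data are needed, and conduct and blinding do not change. The one drawback is that exposure and adverse events then use boundaries one day apart, which the footnote should state.

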### 5.2. Determination of Sample Size

Approximately 150 participants will be randomized in a **CCI** ratio to LY3526318 and placebo, respectively. It is expected that approximately 85%, or 128 participants, will complete the double-blind treatment period of the study. **CCI**

**CCI**

If there is no treatment difference between placebo and LY3526318, the probability of passing the efficacy criterion specified above (ie, false positive) is approximately 0.06. The simulation for the power calculation and sample size determination was carried out using the Fixed and Adaptive Clinical Trial Simulator (FACTS) Version 6.0.

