#### **9.5. Sample Size Determination**

Up to approximately 150 participants will be randomized in a **CCI** ratio to LY3526318 and placebo, respectively. It is expected that approximately 85% of participants will complete the double-blind treatment period of the study. **CCI**

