**CCI**

If there is no treatment difference between placebo and LY3526318, the probability of passing the efficacy criterion specified above (i.e., false positive) is approximately 0.05. The simulation for the power calculation and sample size determination was carried out in FACTS Version 6.0.

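### Protocol 9.5 gives a false-positive probability of about 0.05 and SAP 5.2 gives about 0.06, and the readable text does not say which is current

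*SAP*

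**What the plan says.** Both documents close their sample-size section with the simulated error rate under no treatment difference.

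- Protocol 9.5: "the probability of passing the efficacy criterion specified above (i.e., false positive) is approximately 0.05".
- SAP 5.2: "the probability of passing the efficacy criterion specified above (ie, false positive) is approximately 0.06".

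The surrounding inputs that can be read are these:

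| Input | Protocol 9.5 | SAP 5.2 |
|---|---|---|
| Number randomised | "Up to approximately 150 participants will be randomized in a" (ratio redacted) | "Approximately 150 participants will be randomized in a" (ratio redacted) |
| Completion | "It is expected that approximately 85% of participants will complete the double-blind treatment period of the study" | "It is expected that approximately 85%, or 128 participants, will complete the double-blind treatment period of the study" |
| Software | "The simulation for the power calculation and sample size determination was carried out in FACTS Version 6.0" | "carried out using the Fixed and Adaptive Clinical Trial Simulator (FACTS) Version 6.0" |

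The efficacy criterion to which both sentences refer is redacted in both documents. The protocol's summary of changes lists no change to Section 9.5. The SAP revision history lists only major revisions, to Sections 6.9, 6.15 and 6.17, and does not mention Section 5.2.

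**The concern.** The two sentences appear to describe the same operating characteristic of the same study, in current text, yet they print different values. Nothing readable says that one replaces the other or why they differ.

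The protocol (Section 2.1) describes this as a proof-of-concept study whose data will inform development decisions. The false-positive rate tells the people making those decisions how far to trust a positive result. A reader of the protocol and a reader of the SAP come away with different answers. SAP 6.15 also lets an interim analysis change the final sample size, so the planning value against which such a change would be judged should be unambiguous.

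**Working it through.** **1. What can be reproduced.** The SAP's completer count follows from its own inputs: 150 × 0.85 = 127.5, which rounds to 128. It therefore adds no assumption beyond the protocol's 85%. Neither 0.05 nor 0.06 can be reproduced, because the criterion and allocation ratio are redacted and the other simulation settings are not visible.

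**2. Size of the gap.** The difference is 0.06 − 0.05 = 0.01 and the ratio is 0.06/0.05 = 1.20. At two decimals the figures stand for 0.045–0.055 and 0.055–0.065. The ratio of the unrounded values therefore lies between 0.055/0.055 = 1.00 and 0.065/0.045 = 1.44. The two intervals meet only at 0.055, so a single result rounded consistently to two decimals cannot print as both. Either there were two results or one figure is an error.

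**3. Could two simulation runs differ by this much by chance?** The number of runs is not visible; 1,000 to 10,000 per scenario is assumed. For two independent simulations of n runs each:

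- Variance sum = 0.05 × 0.95 + 0.06 × 0.94 = 0.0475 + 0.0564 = 0.1039.
- Standard error of the difference = √(0.1039/n).

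| Assumed runs n | SE of difference | Gap of 0.01 in SEs |
|---|---|---|
| 1,000 | 0.01019 | 0.98 |
| 5,000 | 0.00456 | 2.19 |
| 10,000 | 0.00322 | 3.10 |

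**4. Chance of printing 0.05 and 0.06 from one true rate.** This is the exact binomial probability that two independent simulations sharing one true rate would print 0.05 and 0.06 in either order, with an exact 0.055 rounded up:

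| Assumed runs n | True rate 0.05 | True rate 0.055 | True rate 0.06 |
|---|---|---|---|
| 1,000 | 0.247 | 0.348 | 0.216 |
| 5,000 | 0.103 | 0.498 | 0.109 |
| 10,000 | 0.024 | 0.500 | 0.031 |

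If the true rate is near 0.055, a split is likely at any of these run counts. If it is at 0.05 or 0.06, a split is plausible with 1,000 runs and unlikely with 10,000. Rounding and simulation error can be neither confirmed nor excluded.

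**5. Could a small change of input produce both figures?** As an illustration only, take a flat-prior normal rule that passes when the posterior probability of an effect larger than a threshold exceeds q, and set the threshold to give a false-positive rate of 0.05 with 150 participants. With 128 participants the same rule gives 0.064 at q = 0.5, 0.059 at q = 0.7 and 0.057 at q = 0.8. A change in the assumed number evaluable could therefore move the rate by about this amount. The rule is assumed, and the documents do not say that such a change was made. The 85% also refers to the whole 8-week double-blind period, whereas SAP 4.1 sets the endpoint at Week 4, so the visible inputs do not fix the number evaluable at the endpoint.

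**The case against.** The strongest reply is that the two figures have not been shown to measure the same thing. The criterion and the allocation ratio are hidden, and if either was revised between the documents, each figure could be correct where it stands. The visible inputs are not word for word the same either: the protocol's 150 is an upper limit and the SAP's is not. Protocol 9.3 makes the SAP the more detailed statistical document, which suggests that 0.06 is the working figure. Both values are approximate planning figures, SAP 6.4 plans no multiplicity adjustment, and the sample size may change at the interim.

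Most of this stands, and it limits the point. It rules out calling either number wrong and keeps the matter minor. It does not remove the mismatch. The SAP's role does not establish that 0.06 supersedes 0.05, and no readable text says so.

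The simulation-error calculation can also be criticised. The probabilities for the order actually printed are half those in the table: about 12%, 17% and 11% at 1,000 runs. At that run count they also depend on how an exact 0.055 is rounded; for a true rate of 0.05 the result is 0.247 if rounded up and 0.206 if rounded down. These are fair qualifications, and the calculation is used only to show that chance cannot be settled either way. Asking for the number of simulations is an optional extra; the point does not depend on it.

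**Conclusion.** The concern holds as a minor cross-document inconsistency. Two current sentences print false-positive probabilities of about 0.05 and about 0.06, on visible inputs that are close to the same, and nothing readable reconciles them. The change records do not settle the matter, particularly as the SAP history covers only major revisions.

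Confidence is high that the printed figures disagree. The cause is open: a changed criterion or input, a transcription error, or rounding with simulation error. The statements about simulation error rest on assumed run counts and on independent simulations. No corrected value can be derived from the public text.

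**What to change.** Check the FACTS record, and re-run the null scenario only if the record does not settle the question. State in SAP 5.2 the single rate that applies to the current criterion and the Week 4 endpoint, preferably with the number of simulations behind it. Then either bring protocol 9.5 into line at its next amendment, or note in the SAP that the protocol figure is superseded and why.

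The cost is a record check, possibly one simulation, and a short text change in the SAP. The protocol need not be amended for this alone. The only downside is that the protocol's stated error rate becomes slightly less favourable if 0.06 is the figure that applies.

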### 5.3. Method of Assignment to Treatment

The method of treatment assignment is described in the CPMP SAP Version 5.

## 6. A Priori Statistical Methods

### 6.1. General Considerations

The estimand for the primary clinical question of interest has been described in the CPMP SAP Version 5.

Unless otherwise specified, efficacy analyses will be conducted for the first 4 weeks of the double-blind period (active treatment phase) and separately for the entire 8-week study. A post-active treatment population will be used for analyses of the last 4 weeks of the double-blind period (post-active-treatment phase) and will include all patients who do not discontinue at or prior to Visit 5. For treatment-emergent adverse events (TEAEs), participants in the post-active treatment population will be analyzed according to the treatment they receive during the active treatment phase. Adverse event (AE) analyses will be reported for the first 4 weeks of the double-blind period (active treatment phase) and separately for the last 4 weeks of the double-blind period (post-active treatment phase). Some AEs may be reported for the entire 8 weeks, if necessary. Laboratory, electrocardiogram, and vital sign results will be reported for the active-treatment phase and separately for the entire 8-week study.

Other general considerations for analyses are described in the CPMP SAP Version 5.

### 6.2. Adjustments for Covariates

The general adjustment strategy has been described in the CPMP SAP Version 5.

### 6.3. Handling of Dropouts or Missing Data

The missing data strategy has been described in the CPMP SAP Version 5.

### 6.4. Multiple Comparisons/Multiplicity

There is no plan to formally adjust for multiplicity.

### 6.5. S S S S Participants

There are no plans to use a modified efficacy subset.

### 6.6. Participant Disposition

The summary of participant disposition has been described in the CPMP SAP Version 5. Disposition will additionally be reported for the first 4-week active treatment period.

### 6.7. Participant Characteristics

The summary of participant characteristics has been described in the CPMP SAP Version 5.

ISA-specific considerations are described below.

#### Michigan Neuropathy Screening Instrument

- Part A - history .1s m . .7)
- Part B - physical assessment subscale (<3 vs .g)

- CCI

## 6.8. Treatment Compliance

Treatment percentage of compliance will be calculated as:

$$\frac{\text{Total pills taken} * 100}{\text{Total pills expected}} \%$$

with total pills taken calculated by total pills dispensed minus total pills returned. A patient is considered to be compliant for a given period if this percentage is between 80% and 120%. Treatment compliance will be reported for the first 4 weeks of the study period (Visit 3 to 5, not including the day of Visit 5), and separately for the last 4 weeks of the study period (Visit 5 to 7, including the day of Visit 5). Note that if a patient misses returning pills at Visit 4 or Visit 5, there will be an issue calculating compliance for the active treatment period, and alternate methods for calculating compliance may be considered. For patients who discontinue early, time after the penultimate visit will be excluded for calculation of treatment compliance. For example, if patient discontinued early at Visit 6, treatment compliance will be derived only from data collected through Visit 5. Comparisons between treatment group for treatment compliance will be performed using a Fisher's Exact test. Listings for treatment compliance of individual patients by treatment period will also be provided.

Depending on the level of observed treatment compliance, and where appropriate, sensitivity analyses of primary endpoints may be conducted by excluding patients with poor treatment compliance.

